5 DATA COLLECTION AND ANALYSIS

[figure not shown]
5.1.1 Data Collection

Phase 1: patient screening:

• Data about initial brief medical history, including pharmacotherapy, screen of AF symptoms, date of birth, sex, ethnicity, address, postcode, telephone number and registered GP/GP surgery address will be recorded directly onto the Edinburgh Napier University secure research drive during participant screening via a specialist university managed laptop. Postcodes will be used to identify Index of Multiple Deprivation (IMD) quintile. There will be no paper records of participant data. Participants will be allocated a unique participant ID at this point. This PID will be the only identifier entered onto the KardiaMobile system, meaning that data stored by KardiaMobile will be anonymous.

 The study nurse will enter the PID into the KardiaMobile station (single lead ECG) (AliveCor Inc) and ask the participant to place their fingers on the KardiaMobile device for 30 seconds

[figure not shown]

 Once the ECG has successfully recorded, the device indicates this, and the study nurse is able to view the ECG on the screen. The ECG is

uploaded to the central KardioPro account (AliveCor Inc) linked to the study by pressing the done button on the screen. AliveCor complies with the EU-U.S. Privacy Shield Framework and the Swiss-U.S. Privacy Shield Framework as set forth by the U.S. Department of Commerce regarding the collection, use, and retention of personal information transferred from the European Union and Switzerland to the United States pursuant to the Privacy Shield. AliveCor has certified to the Department of Commerce that it adheres to the Privacy Shield Principles. Their privacy notice can be viewed at

https://www.alivecor.co.uk/privacy/en/

- In the case of suspected AF or other abnormal rhythm, the study nurse and other study team members are able to view the ECG by logging into the KardioPro account that has been assigned to the project. This allows for the team cardiologist to view any ECGs as required
- Those participants who have abnormal rhythm (AF or otherwise) will be contacted by telephone by the study team one month after they have participated to ensure that they have not been lost to follow-up. We will ask participants whether they have been prescribed of oral anticoagulants, and whether they have been referred to (and attended) a

Date: 30/5/2022 Version: 6

full ECG evaluation and cardiology review [Appendix 12]. If participants have not yet received any follow up, the study nurse will write to the participant's GP informing them of this finding.

Phase 2: healthcare professionals' interview:

Data will be gathered from dental staff and students and GPs involved in the care of patients in the study via individual semi-structured qualitative telephone interviews [Appendix 13] using a University provided encrypted audio device and researchers will make field notes during and after interviews. Interviews topics will include the barriers and enablers to the screening processes in the AF detection programme, and the effects it has had on the reported practice of the healthcare professionals involved with the participant. After the telephone interview, the audio file will be securely shared with a company called 1st Class Secretarial Services https://www.1stclass.uk.com to create a typed document (transcript) of what is said.

5.1.2 Data analysis

Phase 1: patient screening:

Primary analyses will be conducted using SPSS (V26). New episodes of AF will be expressed as true positives divided by total number screened with accompanying 95% CIs. A sample size of 1000 will provide a CI of 60.8% assuming an incidence of 1.6%. χ^2 tests will be used to compare new cases by sex and to identify associations between AF incidence and age group or AF risk factors. A Pearson's or Spearman's correlation test, depending on normality of data, will be used to assess the strength and the direction of relationships between parameters. A two-sided p value of < 0.05 will be considered significant.

Cost-effectiveness

A previously tested decision-analytic Markov model⁸ will be used to simulate the risk of stroke and bleeding events with standard case finding of newly identified AF (i.e. no screening/usual care) and to then assess the impact that screening with single lead ECG would have on the downstream costs and health outcomes over a 30 year time

Edinburgh Napier

horizon. Costs incorporated in the model will include those associated with screening, drugs to offset the risk of stroke (i.e., warfarin or NOACs), adverse events (e.g., systemic embolism, stroke) and the potential complications of warfarin and NOAC treatment (e.g., intracranial haemorrhage, clinically relevant bleed). Health-state utilities associated with pre and post treatment will be incorporated in the model to calculate QALYs. A ceiling ratio of £30,000 per QALY to delineate the cost-effectiveness of opportunistic screening will be applied. Costs and benefits (QALYs) will be discounted at the NICE recommended rate of 3.5% per annum in line with the NICE reference case. Model inputs will be based on several available evidence sources including previous work in AF screening in Scotland. Extensive deterministic sensitivity analysis along with probabilistic sensitivity analysis will be undertaken to investigate model assumption and parameter uncertainty on robustness of the results.

Phase 2: healthcare professionals' interview:

All transcripts and notes from telephone interviews will be thematically analysed using the framework approach⁹ following a five step process to code and categorise the data into key concepts and overarching themes. Two researchers will familiarise themselves with transcripts through reading and re-reading, and by listening to audio-recordings to check accuracy. Using NVivo 20 to organise data, they will openly record preliminary concepts and patterns for four telephone interview transcripts. After discussion between the researchers, an initial analytical framework will be established using agreed codes. Another four transcripts will be analysed before refinement and finalising of the framework to allow comparison within and across cases. A matrix will be created within NVivo 20 to map and explore connections within and between participants and categories. During interpretation, analysis will go beyond descriptions of individual cases to develop themes relevant to explore factors that might influence sustainability of screening processes beyond the study setting.

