1.3 RATIONALE FOR STUDY

Date: 30/5/2022 Version: 6

AF is prevalent, affecting approximately 5% of those aged 65 years and older. Unrecognised AF is generally not associated with symptoms and raised resting heart rate. Those with unrecognised AF usually have stroke risk scores (i.e., CHA2DS2 VASc scores) high enough to warrant anticoagulation. Furthermore, registry data suggests that incidence of AF may be much higher in a population who have periodontal disease, which generates the hypothesis that there are appreciable numbers who would benefit from early recognition of AF through simple detection programmes, followed by thromboprophylaxis to prevent future stroke.

This study aims to determine the appropriateness and impact of dentistry-based screening, using innovative technology (a single/six lead ECG device, KardiaMobile) that has been used in numerous AF screening studies, focused on identifying people with undiagnosed AF, with onward referral to their GP for appropriate medical management of AF. The study also aims to explore the role of dentists in ongoing management of AF, as well their role in raising AF awareness in the public.

The findings of this study will have broad implications for the general population aged 65 years and older with undiagnosed AF. We anticipate that the study will demonstrate that it is possible to identify and treat people in the community, not identified due to COVID-19 restrictions, who were not previously known to have AF, thus greatly reducing the risk of stroke. Findings from this study will inform the design and refinement of a future intervention for large-scale research and implementation.

2 STUDY AIM and OBJECTIVES

2.1 **Aim**

The study aims to test if dental clinics are a suitable place to identify previously undetected AF during and beyond the COVID-19 pandemic. It will determine if there is any correlation between severity of dental disease and AF incidence; test a pathway to ensure that patients are appropriately managed following detection of AF; and determine cost-effectiveness of identification of AF in dental settings.

Primary Objective:

Edinburgh Napier

• To identify the proportion of screened participants with newly identified AF in attending a dental clinic aged 65 years and older.

Secondary Objectives:

- To examine the correlation between periodontal health/disease status; age, sex; ethnicity; Index of Multiple Deprivation; and incidence of AF.

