2.2 Primary Endpoint/Outcome Measure

The primary outcome measure will be the proportion of screened subjects with newly identified AF attending a dental clinic aged 65 years and older.

STUDY DESIGN

(Phase 1) A cross-sectional study of screening in dental clinics to identify undiagnosed AF in adults aged 65 years and over. (Phase 2) A qualitative study of healthcare professionals involved in the care of phase 1 study participants to explore factors that might influence sustainability of screening processes beyond the study setting.

STUDY POPULATION

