2.3 NUMBER OF PARTICIPANTS

All patients attending the Dental Hospital will be eligible to participate if they are aged 65 years or older (n=1000). Additionally, a sub-sample of dental hospital staff/students and general practitioners involved in the care of the participants will be asked to take part in a qualitative telephone interview (n-20).

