2.5 EXCLUSION CRITERIA

The following people will not be eligible to take part in the study:

Phase 1: patient screening:

- Have been diagnosed with severe co-existing conditions (severe dementia or terminal illness)
- Are unable to give informed consent
- Due to time and financial constraints surrounding the cost translation services and qualitative data transcription, the study will be unable to recruit participants who cannot adequately understand verbal explanations or written information given in English

Phase 2: healthcare professionals' interview:

- Dental hospital staff/students who are not working at the Newcastle Dental Hospital and not involved in the care of study participants
- GPs who are not involved in the care of study participants

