- The study team will call the participant approximately 1 month after the date of screening, to ensure they have not been lost to follow-up.
- The study team will call the GP surgery to determine if any treatment or further follow up was required.

Protocol if a diagnosis of AF is not suspected from the screening but an abnormal rhythm is detected

- Those participants with an abnormal rhythm detected on single lead ECG, not previously identified, will be offered a 6-lead ECG on the KardiaMobile. This involves placing an additional electrode on either the left knee or left ankle and takes 30 seconds as for a single-lead recording.
- They will be counselled by the study nurse regarding the diagnosis and advised to return to their GP to discuss the next phase of their management.

- Edinburgh Napier University researchers will send a letter to the GP explaining
 the potential diagnosis, which will include a copy of the 6-lead ECG recording,
 and an invitation to refer their patient for a full assessment at any cardiology
 service of their choosing. A copy will be inserted in the patient notes at
 Newcastle Dental Hospital.
- If the GP refers the participant to the cardiology clinic, the full assessment will be performed by a Cardiologist, according to standard cardiology practice, and will include a 12-lead ECG. If appropriate, the patient may be commenced on appropriate thromboprophylaxis, according to evidence-based guidelines ⁷
- The study team will call the participant approximately 1 month after the date of screening, to ensure they have not been lost to follow-up [Appendix 12].

Protocol if a history of AF is known prior to the screening

 Edinburgh Napier University researchers will send a letter to the participant's GP informing them that their patient was screened for AF, stating if they were in sinus rhythm or AF on the day of the screening.

Linking to periodontal health/disease

 The consent form will include consent for dental hospital staff to provide the Basic Periodontal Examination (BPE) result for each routinely conducted at their appointment (Table 1).

Table 1 E	Table 1 Basic Periodontal Examination		
0	This indicates that there are no pockets >3.5mm (i.e. the black band is completely visible), no bleeding and no calculus or plaque traps (e.g. overhanging restorations)		

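### The denominator for newly identified AF includes people already known to have AF, so the yield of undiagnosed AF is slightly understated

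*Combined protocol and SAP*

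**What the plan says.** Section 2.2 defines the endpoint: "The primary outcome measure will be the proportion of screened subjects with newly identified AF attending a dental clinic aged 65 years and older". The primary objective in section 2.1 is worded in the same way. Section 5.1.2 turns this into an estimator: "New episodes of AF will be expressed as true positives divided by total number screened with accompanying 95% CIs".

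Section 2.3 opens the study to every Dental Hospital attender aged 65 or over. Neither the inclusion criteria (2.4) nor the exclusion criteria (2.5) mention AF history. The only diagnosis-based exclusion reads: "Have been diagnosed with severe co-existing conditions (severe dementia or terminal illness" (closing bracket omitted).

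Section 4.1 has a separate pathway headed "Protocol if a history of AF is known prior to the screening". Under it, the GP is told that the patient was screened and which rhythm was seen that day. Appendix 11 records AF under medical history and also gives previously known AF its own line among the ECG results.

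The study design statement gives the purpose of phase 1 as finding undiagnosed AF. No section removes people with known AF from the denominator or allows for them in the 1000.

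**The concern.** A person with known AF can be recruited, screened and counted in the total, but cannot be a newly identified case. The reported proportion therefore mixes two things: how often screening finds AF in people who could be newly diagnosed, and how many attenders already carry the diagnosis. The second depends on the case mix of one dental hospital. More recruitment does not remove it, and it makes the result harder to compare with other settings.

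The secondary analyses may be affected too. Sections 2.1 and 5.1.2 plan to relate new AF to age, sex, risk factors and periodontal status, and name no other denominator for these tests. If known AF is more common in one group than another, the new-case rate in that group is diluted more. A difference can then appear, shrink or reverse for reasons unrelated to undiagnosed AF.

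**Working it through.** **Inputs.** Section 5.1.2 gives 1000 screened, an assumed rate of 1.6% and a 95% interval (z = 1.96). This implies 0.016 × 1000 = 16 new cases. The known-AF share, k, is not stated anywhere. Section 1.3 offers a general figure, "AF is prevalent, affecting approximately 5% of those aged 65 years and older", without saying whether it counts diagnosed AF only. It serves here only as an illustration, within an assumed range of 2% to 10%.

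**Step 1: the plan's own precision.** The text reads "A sample size of 1000 will provide a CI of 60.8% assuming an incidence of 1.6" (per cent). The printed interval is taken as ±0.8%, with the first character misread in text extraction. The Wald half-width is 1.96 × √(0.016 × 0.984 / 1000) = 0.778 points, which rounds to 0.8. The stated precision therefore reproduces with all 1000 in the denominator.

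**Step 2: size of the dilution.** With x new cases among N screened, the plan reports x/N. The yield among those without known AF is x/[N(1 − k)]. The ratio of the first to the second is 1 − k, so the relative understatement equals k.

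**Step 3: numbers.** Here n = 1000(1 − k) is the number without known AF, and half-widths are in percentage points.

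| Assumed k | n | 16/n | Half-width at 16/n | Half-width at fixed 1.6% | Screened to reach n = 1000 |
|---|---|---|---|---|---|
| 0 | 1000 | 1.60% | 0.78 | 0.78 | 1000 |
| 2% | 980 | 1.63% | 0.79 | 0.79 | 1021 |
| 5% | 950 | 1.68% | 0.82 | 0.80 | 1053 |
| 10% | 900 | 1.78% | 0.86 | 0.82 | 1112 |

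The exact (Clopper–Pearson) 95% interval is 0.92% to 2.59% for 16/1000 and 0.97% to 2.72% for 16/950.

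If 1.6% is instead the rate among people without known AF, the plan's estimator would be expected to return 1.6% × (1 − k): 1.57%, 1.52% and 1.44% for k = 2%, 5% and 10%.

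If the 5% is total AF and 1.6 points of it are undiagnosed (a further assumption), known AF is 3.4% and the yield is 16/966 = 1.66%.

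**Step 4: group comparisons.** Suppose two groups have the same 1.6% yield among people without known AF, but known-AF shares of 3% and 12% (assumed). The all-screened rates are 1.6% × 0.97 = 1.55% and 1.6% × 0.88 = 1.41%. The gap comes entirely from the denominator.

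**The case against.** The strongest reply is that the plan is consistent with itself. Sections 2.1 and 2.2 ask for the proportion of screened participants with newly identified AF, and section 5.1.2 estimates exactly that. For a service offered to every attender aged 65 or over, new cases per person screened is a legitimate quantity, and the estimator is not biased for it. This stands. What remains is that this quantity does not answer the question about undiagnosed AF as directly as a yield among people without the diagnosis.

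The second reply is size. At 5% the shift is 0.08 points, about a tenth of the planned half-width. This also stands.

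Four stronger readings are tempting, but the documents do not support them:

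- **A known-AF share of 13% or 16%.** A reader might take these from section 1.1. There they describe AF found in cohorts assessed without prior AF (754 of 5,958 and 1,558 of 9,666), so they say nothing about how many attenders already have a diagnosis.
- **A failed precision statement.** Section 5.1.2 bases its interval on 1000 people screened, not 1000 without known AF, and the figure reproduces.
- **A corrupted cost-effectiveness model.** No section says that this proportion enters the Markov model. Section 5.1.2 says that inputs come from several evidence sources, including earlier Scottish work.
- **A restriction to readable traces.** The known-AF argument gives no reason for it, and Appendix 11 has no result line for an unreadable trace.

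**Conclusion.** The point holds in a limited form. The denominator includes people who cannot be new cases. As a yield among people without known AF, the reported figure is too low by a relative amount equal to the known-AF share. At an assumed 5% that is 1.60% against 1.68%; over an assumed 2% to 10% it is 1.60% against 1.63% to 1.78%. At a fixed 1.6% the half-width stays between 0.78 and 0.82 points. The direction follows from the text, but the size rests on a share that the documents do not give.

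Unequal dilution of the group comparisons is conditional on known AF differing between groups, which is not quantified either. A reader might infer that the primary estimate is invalid. It is not: it is correct for its stated endpoint. This is a cheap improvement, not a fault that must be cured before the study can proceed.

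**What to change.** In sections 2.2 and 5.1.2:

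- Define the yield of undiagnosed AF on screened participants with no history of AF before screening, as recorded in Appendix 11.
- Run the association tests for new AF on the same participants.
- Report the all-screened proportion alongside, and known AF as a separate count.
- Note that the 1000 includes people with known AF, so slightly fewer could be newly identified.
- If the study yield is used in the cost-effectiveness model, take the yield and the screening costs from the same population. Removing known AF from the yield while ignoring the cost of screening those people would flatter screening.

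Settle this before the data are analysed, so that the denominator is not chosen after the result is seen.

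The cost is a change of wording. AF history is already collected, and neither recruitment nor procedures change. The price is a slightly smaller denominator and a marginally wider interval.

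Suggested wording for 5.1.2: *The yield of undiagnosed AF is the number of newly identified cases divided by the number of screened participants with no recorded history of AF, with a 95% CI. New cases as a proportion of all screened participants, and the number with known AF, will also be reported.*

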4 STUDY PROCEDURE

4.1 STUDY ASSESSMENTS

Phase 1: patient screening:

The study nurse will complete the following screening protocol:

- The screening will be approximately 5min duration.
- Screening will consist of an initial brief medical history, including pharmacotherapy and screen of AF symptoms. We will also ask for date of birth, sex, ethnicity, postcode so that we can link Basic Periodontal Examination to participants. We will also ask for telephone number and registered GP/GP surgery address only in the case of abnormal rhythm or inconclusive rhythm so that we are able to inform the GP of results and follow up participants [Appendix 11].
- The study team will assess cardiac rhythm using the single-lead recording function on the handheld KardiaMobilie ECG device for 30s. The KardiaMobile ECG device will be the property of ENU and will be in the possession of the study nurse during assessments. The device will not be on participants personal mobile telephones.
- The ECG record with a unique identification number will be transmitted by wireless connection on a secure server to an iCloud by the KardiaMobile software. The ECG record is only accessible by the study team.
- The study team will advise the participant of the suspected diagnosis and ensure they understand the next steps in the pathway
- For every person with an abnormal ECG (not AF), the study team will offer a 6-lead ECG using the KardiaMobile 6-lead functionality. KardiaMobile

Date: 30/5/2022 Version: 6

records Leads I,II,II, AVL, AVR, and AVF by additional electrode placement on left knee or ankle.

At the end of the screening, participants will be given a participant debrief sheet [Appendix 10] and those with a normal rhythm will be given a letter stating that no further action is required [Appendix 16].

Protocol if AF is not suspected from the screening

GP will not be informed of the participant screening.

Protocol if a diagnosis of AF is suspected from the screening

• The study nurse will counsel the participant and advise that their GP will be contacted to arrange follow up.

- Edinburgh Napier University researchers will send a typed letter to the GP explaining the potential diagnosis, which will include a copy of the ECG recording. If required, the letter will include an invitation to refer their patient for a full assessment at any cardiology service of their choosing. A copy will be inserted in the patient notes at Newcastle Dental Hospital.

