12.11 Appendix 11: Patient Screening Document Phase 1 (Version 3:16/8/2022)

	Participant ID:			
	Name			
	Address			
	Postcode (IMD):			
	Date of Birth:			
	Telephone Number:			
	Registered GP:			
	GP surgery address:			
		l		
٧	Vhat sex where you a	ssigned at bir	th?	
	Male			
	Female			
V	What age are you?			
•	viiat age are you:			
٧	Vhat race/ethnic grou	p do you cons	ider yourself	?
	White British			
	White Other			
	Black Caribbean/Black Ca	ıribbean		
	British			
	Black African/Black Africa	an British		
	Indian/Indian British			
	Pakistani/Pakistani Britisl	h		
	Bangladeshi/Bangladeshi	British		
	Chinese/Chines British			
	Filipino/Filipino British			
	Maghreb / Middle Easter	'n		
	Mixed Ethnicity			
	Other (please specify)			
L)o you have / a histor y Heart Failure	y of any of the	following?	
		ا مسمممیسم)		
	Hypertension (high blood	•		
	Stroke/TIA/thromboemb			
	Vascular disease (prior M	• •		
	artery disease or aortic p	iaque)		
	Diabetes			
	Atrial fibrillation			

Are you taking any of the medication b	e low?
Warfarin	
Dabigatran	
Rivaroxaban	
Edoxaban	
Apixaban	
Beta-blocker (ends in IoI)	
Verapamil	
Diltiazem	
Amiodarone	
Flecainide	
Propafenone	
Digoxin	
Other (please specify)	
Do you have any of the following symp	toms?
Heart palpitations	
Chest pain	
Dizziness	
Fatigue	
Light-headedness	
Shortness of breath	
Reduced ability to exercise	
None	
	Screening
KardioMobile ECG Screening	Result
Sinus rhythm	
AF not suspected by abnormal rhythm	
AF suspected	
AF known prior to screening	
Basic Periodontal Examination	Result
Upper right Upper anterior Upper	1
Lower right Lower anterior Lower	
Lower differior Lower	

Appendix 12 : Follow up telephone screening form Phase 1 Study Protocol Date: 25/1/2022 Version: 5

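### The only test named for age is an unordered chi-square on undefined age groups, although age in years is held; if risk rises steadily with age, this loses some power on about 16 expected cases

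*Combined protocol and SAP*

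**What the plan says.** The secondary objective in section 2.1 is "To examine the correlation between periodontal health/disease status; age, sex; ethnicity; Index of Multiple Deprivation; and incidence of AF". It lists age, not age group.

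The analysis in section 5.1.2 (Phase 1) assigns age to a chi-square: χ² "tests will be used to compare new cases by sex and to identify associations between AF incidence and age group or AF risk factors". It gives no number of groups, no cut points, no trend test and no reason for grouping. The next sentence plans a Pearson or Spearman correlation, chosen by normality, between parameters that it does not name. No regression on age is planned. The significance rule is "A two-sided p value of < 0.05 will be considered significant".

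Age is available in years. Section 4.1 says "We will also ask for date of birth, sex, ethnicity, postcode so that we can link Basic Periodontal Examination to participants", section 5.1.1 lists date of birth among the recorded data ("Data about initial brief medical history, including pharmacotherapy, screen of AF symptoms, date of birth, sex, ethnicity, address"), and the screening form in Appendix 11 also asks "What age are you".

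**The concern.** A chi-square on age groups discards age differences within each group. With three or more groups it also ignores their order, and spends 2 to 4 degrees of freedom (for three to five groups) on a question that one degree of freedom can answer. With two groups there is one degree of freedom and order plays no part, but the information within groups is still lost.

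This matters because cases are few. Age bears on who would gain from screening in a dental setting, and a real gradient could be reported as no association with age group. Undefined groups also leave the cut points open until the data are seen; with about 16 cases, one or two falling on the other side of a boundary could change the result.

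**Working it through.** **Inputs from the plan (section 5.1.2).** n = 1000; new AF 1.6%; two-sided 5%.

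**The plan's own figure.** The text reads "A sample size of 1000 will provide a CI of 60.8% assuming an incidence of 1.6"%. The Wald half-width is 1.96 × √(0.016 × 0.984 / 1000) = 0.0078, or 0.78 points. This agrees with ±0.8% if the printed 6 is a misread plus-minus sign. Expected cases: 1000 × 0.016 = 16. The plan states no power for the age comparison, so there is none to reproduce.

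**Assumptions not in the documents.** Age distribution, age effect and cut points. In the first simulation, ages run from 65 to 95 with density proportional to exp(−(age − 65)/m), m = 8 or 10. New AF follows a logistic model, linear in age, calibrated to 1.6% overall. There are 6000 replicates per scenario, so the Monte Carlo standard error of one power figure is at most √(0.25/6000) = 0.6 points. The score test on age in years uses N × r² on 1 df, where r is the Pearson correlation of age with AF coded 0/1.

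Power in %, m = 8 / m = 10:

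| OR per 10 years | Five 5-year groups | Three 10-year groups | Cut at 75 | Age in years, score test | Gain, points |
|---|---|---|---|---|---|
| 1.5 | 21.5 / 21.3 | 23.4 / 24.5 | 19.0 / 20.3 | 26.2 / 28.4 | 2.8 to 8.1 |
| 2.0 | 49.0 / 49.9 | 53.0 / 55.5 | 45.6 / 48.8 | 60.0 / 64.8 | 7.0 to 16.0 |
| 2.5 | 72.8 / 73.8 | 75.8 / 78.8 | 69.0 / 71.8 | 83.1 / 86.3 | 7.3 to 14.5 |
| 3.0 | 85.9 / 87.9 | 87.9 / 90.7 | 82.4 / 86.1 | 92.8 / 95.3 | 4.6 to 10.4 |

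The gain is the score-test power minus the grouped power at the same m; for example, 60.0 − 53.0 = 7.0 and 64.8 − 48.8 = 16.0. With no age effect, all tests rejected in 4.7% to 5.4% of runs.

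**Dependence on the test used for age in years.** The same set-up was re-run with 4000 replicates at OR 2.0. The grouped tests gave 47.3 / 47.1, 50.8 / 52.8 and 44.4 / 45.8.
- The likelihood-ratio test, which matches a profile-likelihood interval, gave 53.3 / 56.6. The gain is 53.3 − 50.8 = 2.5 to 56.6 − 45.8 = 10.8 points. A further run gave about 2 to 11.
- At OR 2.5 the likelihood-ratio gain was about 3 to 12 points. At OR 1.5 it was about −2 to +5 over two runs.
- The Firth-penalised test at OR 2.0 gave 57.4 / 59.7, a gain of 57.4 − 50.8 = 6.6 to 59.7 − 45.8 = 13.9 points.

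**Dependence on the age distribution.** Score test against five groupings, with two to five groups:
- Half-normal from 65, OR 1.08 per year (1.08^10 = 2.16 per 10 years): 55.8 against 40.8 to 47.3, a loss of 8.5 to 15.0 points.
- Truncated normal, mean 74, OR 1.09 per year (2.37 per 10 years): 47.7 against 29.0 to 39.2, a loss of 8.5 to 18.7. At 1.12 per year (3.11 per 10 years): 70.1 against 46.8 to 57.2, a loss of 12.9 to 23.3.
- Uniform 65 to 90, OR 1.08 per year: 55 against 27 to 44, a loss of 11 to 28.
- Over all log-linear scenarios run, the loss was about 1 to 32 points.

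**Where the loss comes from.** With five 5-year groups, a 1-df trend test on the groups came within about 0 to 4 points of age in years. In the half-normal case at 1.08 per year, the unordered chi-square gave 46.0, the trend test 52.6 and age in years 55.8. With several groups, most of the loss comes from ignoring order.

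**Dependence on log-linearity.** With a step at age 75 (OR 3, m = 8), the grouped tests gave 51.2 to 62.1, against 48.8 (score), 43.6 (likelihood ratio) and 47.6 (Firth). A repeat gave 49 to 60 for groups against 40 to 46 for age in years. The ranking reverses.

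**The case against.** The strongest reply is that the better test may already be planned. The objective speaks of correlation and lists age, and the sentence after the chi-square plans a Pearson or Spearman test. A Pearson correlation of age with AF coded 0/1 is essentially the score test used above. A reader might infer that the plan analyses age only in groups; the documents do not settle that. Nor do they say that age is one of the correlated parameters, or which variable's normality decides the choice. If the rule leads to Spearman, which a yes/no outcome makes likely, power at OR 2.0 was 48.4 / 55.4, close to the grouped tests. Under other age shapes Spearman recovered part or all of the loss. The sentence leaves an ambiguity and does not answer the point.

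The second reply is that log-linear scenarios favour a log-linear test, and that the gain shrinks with the likelihood-ratio test. Both stand, and the verdict reflects them.

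Third, this is one factor in a secondary objective with no stated power, and a trend test on several pre-defined groups would recover most of the loss. That also stands, but the plan neither defines the groups nor names such a test.

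A reader might also infer that sparse groups make the chi-square invalid. With exponential ages and no age effect, five groups expect 7.9, 4.1, 2.1, 1.1 and 0.8 cases. Even so, null rejection was 4.4% to 5.8% for all tests over the runs, so the simulations show lost power and no inflated error rate.

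**Conclusion.** The point holds as a shortfall in a secondary analysis. The plan names an unordered chi-square on undefined groups for a variable that it holds in years. Under a log-linear age effect at OR 2 to 2.5 per 10 years, with ages falling off exponentially from 65, the loss is about 7 to 16 points against a score test on age in years. It is about 2 to 12 points against a profile-likelihood logistic test. For those age shapes the loss is smaller at OR 1.5 and OR 3.0; for other shapes it can be larger and peak elsewhere. If risk rises as a step, the grouped test can do better.

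A reader might take 7 to 16 points as a property of the plan. It is not: the age distribution, odds ratio and cut points are all assumed. Nor does the scale of age by itself decide whether a gradient is seen. In the table every test is below 29% at OR 1.5 and above 82% at OR 3.0. The primary proportion and its interval are unaffected.

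**What to change.** In section 5.1.2:
- Make the main test for age a 1-df score (linear trend) test of newly identified AF on age in years at screening, calculated from date of birth.
- Report the logistic odds ratio per 5 or 10 years with a Firth-penalised 95% CI. State that the p value comes from the score test, since the two can disagree near 0.05.
- Keep an age-group table with cut points fixed in advance, counts and exact 95% CIs, as description and as a check of linearity. With about 16 cases that check is rough.
- Say which variables the Pearson/Spearman sentence covers.

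The cost is a few sentences of analysis wording, with no new data, participants or procedures. The plan names SPSS V26; whether the team's installation offers Firth estimation should be confirmed. The statistical price is an assumed log-linear age effect, which loses power if the true pattern is a step.
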